3.3. Type and Planned Number of Participants

Participants will be recruited from schools in the areas of the study centre. Study staff may address parents/Legally Acceptable Representatives (LARs) in parents-teachers' meetings. It is not anticipated that any advertising such as posters, leaflets, radio, etc. will be required to aid recruitment. However, these methods may be used if required.

Approximately 1300 participants will be screened in at least 4 schools (with at least 2 schools per study group), to randomise approximately 924 participants to ensure 646 evaluable participants complete the entire study. This will ensure at least 323 evaluable participants per study group.

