Background diets and changes in background diets may distort the true relationship between the intervention and the outcome. To eliminate such possible confounding, it is imperative that quality of dietary intakes is assessed both at start and end of study. Since, quality of a diet is impacted by food quantity and diversity; both these variables will be assessed for all study participants. For quantitative assessment of food consumption, 24-hour dietary recall will be used. To understand the diversity of foods that the child is consuming, a 24-hour Individual Dietary Diversity Score (IDDS) [FAO guidelines dietary diversity, 2011] will be used.

Cluster sampling design may impact effective sample size, which can be mitigated using more numbers of clusters. Thus, considering feasibility, at least 2 schools per study group will be selected.

To control for possible effects of gender, a balanced ratio of boys and girls in the test and control groups will be targeted. The study will be stratified by gender to recruit a target ratio of 50% girls and 50% boys, with a minimum of 40% of either gender and a maximum of 60% of either gender.

 GlaxoSmithKline	Document Name	Clinical Study Protocol 204477		
	Type	Version	Document Identifier	Effective Date
	eldo_clinical_doc	5.0; Most-Recent; Effective; CURRENT	090032d580daa95e	10-Oct-2017 06:16:49
	Reason For Issue	Auto Issue		

The study flowchart will be as follows:

 GlaxoSmithKline	Document Name	Clinical Study Protocol 204477		
	Type	Version	Document Identifier	Effective Date
	eldo_clinical_doc	5.0; Most-Recent; Effective; CURRENT	090032d580daa95e	10-Oct-2017 06:16:49
	Reason For Issue	Auto Issue		

Rationale for Participants' Inclusion and Exclusion:

With the assumption that the study population is normally distributed for World Health Organisation (WHO) height-for-age z-scores (HAZ), reference populations within -2 to +2 standard deviations (or z score) represent 95.4 % population. But for the study participants in developing countries like India, the median for the HAZ in comparison to WHO growth standards is towards the lower side which falls at approximately -2 SD of the WHO standard curve at age 5 years [National Family Health Survey -3] [Indian Academy of Paediatrics Growth Charts Committee, 2015]. Thus a Z-score between -3 to -1 (rather than -2 to +2) would cover the representative population of developing countries like India.

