5.9.1 Randomisation

A unique screening number will identify each participant screened for study participation. At each school, screening numbers will be assigned in ascending numerical order as each participant's parent/LAR signs their consent form.

This study will follow cluster randomisation where in schools will be termed as clusters and then matched pairs will be formed on the basis of criteria defined in Section 6.1. As schools are determined to be fully eligible and matched pairs are formed, schools within the matched pairs will be randomised according to the randomisation schedule provided to the study centres. Each matched pair will be assigned a randomisation number in ascending numerical order as each matched pair is formed.

Once 60% of participants from any gender have been enrolled within a study group, recruitment into that gender will stop to ensure that there is a maximum 60% of either male or female. Remaining 40% of participants will be recruited from other gender.

The randomisation schedule will be provided by the Biostatistics Department, GSKCH.

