6.1. Matched Pair Formation

Each school will be deemed as a cluster. Schools with following characteristics will be invited to participate in the study:

- ~~Located in peri-urban areas~~
- No government or sponsored micronutrient supplementation scheme running in past 6 months
- Mixed-gender education/co-education system of education
- No history of any outbreak or clustering of cases of infectious diseases in last month

Schools which agree to participate will be selected and will be subsequently matched for cluster size (in context to the number of children in 7-10 yrs age group), socioeconomic profiles of students, and type of school; government subsidised or private.

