9. STATISTICAL CONSIDERATIONS AND DATA ANALYSES

9.1 Sample Size Determination

The primary efficacy variable of the study is the total number of ill days due to GI and respiratory illnesses. The sample size has been calculated based on the assumption of an average of 7 ill days in the control group with a difference of 10% between the treatments.

 GlaxoSmithKline	Document Name	Clinical Study Protocol 204477		
	Type	Version	Document Identifier	Effective Date
	eldo_clinical_doc	5.0; Most-Recent; Effective; CURRENT	090032d580daa95e	10-Oct-2017 06:16:49
	Reason For Issue	Auto Issue		

Years Lost due to Disability (YLD) is a measure of the burden of disease from its morbidity. Below are data that are specific to India: As per the data from Global Burden Disease, WHO 2010 study (GBD, WHO, 2012; IHME, 2013) and Census India, 2011, YLD per child in the 5-9 year age group, due to diarrhea, LRTIs, other infectious disease and nutritional deficiencies is 8.274 days/child per year or 6.21 days/child per 9 months.

Thus, based on above data, approximately 7 ill days due to GI and respiratory illnesses per 9 months has been assumed in this proposed study population of 7-10 year olds.

The sample size is based on the primary endpoint. No sample size considerations have been taken into account for secondary objectives.

The simulated data were also used based upon the assumption of a Poisson distribution per study treatment. On observation of these simulated data, it was considered that these Poisson distributions were not heavily skewed and, as a result, normal distributions may be assumed. Consequently, a normality assumption has been adopted for both the generation of sample size and the intended approach to the statistical analysis.

Because of assumption of poisson distribution, estimates of variability were calculated as square root of mean.

Mean of control was assumed to be 7.0 and standard deviation (SD) was 2.65, mean of test group was 6.3 and SD was 2.51. To be able to achieve 80% power, 215 participants per treatment arm (Total = 430) will be required to complete the study in case of individual randomisation. This assumes 5% level of significance (two tailed t-test).

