As this study is using cluster randomisation, and design effect (DE) needs to be considered for sample size calculations. Scientific literature suggests, DE due to cluster sampling strategy can be assumed to be 1.5 [Rosner, B, 1986]. Same has been assumed in one study, which used three-stage systematic cluster sampling [Dandona R *et al*, 2008].

Using the following formula from Hemming *et al*, 2011:

$$N^* = N \times DE$$

Where N*=Number of participants required for cluster randomised trial

 GlaxoSmithKline	Document Name	Clinical Study Protocol 204477		
	Type	Version	Document Identifier	Effective Date
	eldo_clinical_doc	5.0; Most-Recent; Effective; CURRENT	090032d580daa95e	10-Oct-2017 06:16:49
	Reason For Issue	Auto Issue		

N = Number of participants required for individual randomisation

DE = Design Effect

And assuming DE to be 1.5, the number of evaluable participants completing the study required would be 323 per arm (Total=646).

To allow for 30% drop-out rate, a total of 924 participants will be randomised.

Approximately 1300 participants will be screened to randomise approximately 924 participants in order to obtain 646 participants completing the study.

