3.3 Centers Pools

This study is conducted in multiple (4) schools, with two schools in each product group.

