4.4.1.2 Statistical Hypothesis, Model, and Method of Analysis

For the primary variable, primary analysis will be performed on participants on the mITT population.

The null hypothesis of interest is:

H0: There is no difference between the numbers of illness days for the product groups.

The alternative hypothesis of interest is:

H1: There is a difference in between the numbers of illness days for the product groups.

The number of ill days will be analysed using the analysis of variance (ANCOVA) model. The ANCOVA will have cluster (school) as a random effect, product group and gender as fixed effects and baseline IDDS as a covariate.

Adjusted means, 95% confidence intervals (CI), within product group p-values for each product group, product group difference, intracluster correlation, 95% confidence interval of the difference and the between-product group p-values based on the statistical model described above will also be presented ([Table 14.2.2.2](#)).

All statistical tests of hypotheses will be two-sided and will employ a level of significance of $\alpha = 0.05$.

The simulated data used for the sample size calculations were based upon the assumption of a Poisson distribution per product group. However, on observation of these simulated data, it was considered that these Poisson distributions were not heavily skewed and, as a result, normal distributions may be assumed. Consequently, a normality assumption has been adopted for both the generation of sample size and the intended approach to the statistical analysis.

However, the assumptions of normality and homogeneity of variance will be investigated and violation of these assumptions may be overcome using suitable transformation (for example, log or square root or Poisson regression using Proc Genmod) or by performing appropriate non-parametric tests (e.g., Van Elteren, rank ANCOVA).

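### A design effect of 1.5 does not preserve 80% power with four schools: a between-school test on 2 df has about 35%, and the SAP never names the df

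*Protocol*

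**What the plan says.** Protocol 9.1 assumes 7.0 ill days (SD 2.65) in control and 6.3 (SD 2.51) in test. With a two-tailed 5% t-test and 80% power it finds that "215 participants per treatment arm (Total = 430) will be required to complete the study in case of individual randomisation". It then applies N* = N × DE: "And assuming DE to be 1.5, the number of evaluable participants completing the study required would be 323 per arm (Total=646"). SAP 1.4 repeats this. The number of schools does not enter the calculation, and no intracluster correlation (ICC) or school size is given.

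On the number of schools, Protocol 3.3 says that participants "will be screened in at least 4 schools (with at least 2 schools per study group), to randomise approximately 924 participants". Protocol 3.4 concedes that more clusters would mitigate the loss of effective sample size, then says "Thus, considering feasibility, at least 2 schools per study group will be selected". The SAP is definite: "This study is conducted in multiple (4) schools, with two schools in each product group".

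The school is the unit of allocation (Protocol 5.9.1): "schools within the matched pairs will be randomised according to the randomisation schedule provided to the study centres". For the primary test, SAP 4.4.1.2 states: "The ANCOVA will have cluster (school) as a random effect, product group and gender as fixed effects and baseline IDDS as a covariate". Amendment 1 introduced the random effect on the ground that adjustment for intracluster correlation is needed for validity. Neither document names a denominator df method, a cluster-level test or a small-sample correction.

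**The concern.** A design effect says how much larger the variance of the treatment difference is. It does not say how well that variance is estimated. With two schools per arm, the variation between schools within an arm is estimated on 2 df. If the matched pairs were kept in the analysis, it would be 1 df. The 80% figure relies on a critical value near 1.96, which such a test does not have.

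Two things are at stake. The trial is presented as adequately sized for a 10% reduction when a test that respects the design is not. Protocol 9.2.3 also defines success as a statistically significant decrease on this endpoint. A software setting that the SAP leaves open could therefore decide whether the same data count as success.

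**Working it through.** **Inputs (Protocol 9.1, SAP 1.4, SAP 3.3).** Difference 0.7 days; SDs 2.65 and 2.51; two-sided α 0.05; DE 1.5; 323 evaluable per arm; two schools per arm. Equal school size (323/2 = 161.5) is an assumption.

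**The plan's own figures.**
- Average variance v = (2.65² + 2.51²)/2 = 6.66.
- 215 per arm, individually randomised: power 80.1%.
- 215 × 1.5 = 322.5, rounded up to 323 per arm, 646 in total.
- 323/0.7 = 461.4, rounded up to 462 per arm, 924 in total.

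The participant numbers reproduce.

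**Power with the schools counted.**
- SE = √(2 × 6.66 × 1.5/323) = 0.2487; noncentrality = 0.7/0.2487 = 2.81.
- Noncentral t power:

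| df | critical t | power |
|---|---|---|
| 642 (individual level) | 1.96 | 80% |
| 2 (four schools, two arms) | 4.30 | 35% |
| 1 (two matched pairs, same SE) | 12.7 | 17% |

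- Difference detectable with 80% power on 2 df: 1.41 days, and 1.41/7.0 = 20%.
- With no clustering at all (DE 1.0), a 2-df test still has only 47% power.

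**Implied ICC.** DE = 1 + (m − 1) × ICC, so ICC = 0.5/(161.5 − 1) = 0.0031. Other ICCs are assumptions, not in the documents. With two schools per arm, 0.005, 0.01 and 0.02 give 31%, 24% and 17% on 2 df.

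**Number of schools (323 children per arm, unpaired).**

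| schools per arm | 2 | 3 | 4 | 6 |
|---|---|---|---|---|
| power, DE held at 1.5 | 35% | 57% | 65% | 72% |
| power, ICC held at 0.0031 | 35% | 62% | 73% | 82% |

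**What the unstated df rule does.** 400,000 simulated trials: normal outcomes, equal schools, DE 1.5, no covariates.

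| analysis | power at 0.7 days | Type I error |
|---|---|---|
| random school, residual df | 76% | 7.0% |
| random school, 2 df if school variance is positive, residual df if zero (Satterthwaite-type) | 46% | 5.3% |
| t-test on school means, 2 df | 35% | 5.0% |
| random school, variance bounded at zero, always 2 df | 14% | under 0.1% |

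At assumed ICCs of 0.01 and 0.02, Type I error rises to 11.6% and 14.6% on residual df, and to 7.1% and 7.4% under the Satterthwaite-type rule. At DE 1.5 the school variance is estimated at or below zero in about 49% of trials, although clustering is present.

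**Unequal schools.** For the school-means test with assumed sizes of 200/123 or 242/81 in each arm, 2-df power is 34% or 31% and Type I error 4.9% or 4.5%.

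**The case against.** The strongest reply is that 35% is not the power of the SAP's model as written. It belongs to a school-means t-test on 2 df, whereas the SAP fits a random-school ANCOVA with no df named. This is right as far as it goes, and the 35% must always be quoted with its condition. It does not rescue the 80%: none of the df options simulated for that model reaches it, and the nearest (76%) exceeds 5% Type I error. SAP 4.4.1.2 also allows Poisson regression and rank tests with no school term stated. A normal-data analogue that ignores school rejects 88.6% of the time at 0.7 days, but with 10.9% Type I error, so it is not a valid route to 80%.

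A Satterthwaite-type rule is a fair rival: 46% power and 5.3% Type I error at the plan's DE. It loses control only at higher, assumed ICCs. Since the ICC is unknown and four schools can barely estimate it, that is a poor basis for the confirmatory test.

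The protocol does say at least four schools, so its figure should be labelled as that for the minimum; SAP 3.3 says four. Nor are 215, 323 and 924 miscalculated. The fault is that the number of clusters was left out.

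**Conclusion.** The concern holds. The participant numbers are right for the formula used, but the 80% power does not carry over to four schools. Taking DE 1.5 as true and schools as equal in size, a between-school test that holds 5% has about 35% power on 2 df, or 17% on 1 df if the pairs are kept. The detectable difference is about 20%, twice the one planned for. A higher ICC or unequal schools would lower the power further. The missing df rule is a separate gap: it moves power from about 14% to 76% on the same design, so it has to be fixed before analysis. This must be corrected.

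**What to change.** 1. **Power statement.** In SAP 1.4, say that the four-school design has about 35% power for a 10% difference at DE 1.5 when tested on 2 df, with a detectable difference of about 20%. In Protocol 9.1, give the same figure as that for the minimum of two schools per group. Change both together, because SAP 1.4 summarises the protocol. Add a table over assumed ICCs (0.003 to 0.02) and schools per arm (2, 3, 4, 6), with equal school size stated as an assumption.
2. **Primary test.** In SAP 4.4.1.2, make the success test a two-sided t-test on the four covariate-adjusted school means with 2 df, and put the 95% CI on the same 2 df. Take the means from an individual-level model with school as four fixed levels, gender and baseline IDDS. Do the same for the other ANCOVAs, with their own covariates, and for any transformed outcome. State that the model has no pair term and that keeping the pairs would leave 1 df. The Poisson and rank fallbacks and the MMRM (SAP 4.4.1.3) also need a stated treatment of school and df.
3. **Random-school model.** Keep it for estimation and the reported ICC, but do not declare success from it on individual-level df. An unbounded-variance REML fit should not be the primary test either. Schools are matched on size only within pairs (Protocol 6.1: they "will be subsequently matched for cluster size (in context to the number of children in 7-10 yrs age group")), and with unequal schools in each arm its Type I error on 2 df was 10.6% to 32.4% in simulation when fits at the variance limit were accepted.
4. **Table 14.2.2.2.** Footnote that, with four schools, an estimated ICC of zero is not evidence of no clustering.

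**Cost.** Wording, one table and one test specification; no extra children. Stating the power does not raise it. Only more schools would, and that is a design change. The CI widens to an expected half-width of about 0.95 days, against about 0.5 on individual-level df (1.96 × 0.2487 = 0.49). With a true 0.7-day effect at DE 1.5, about 93% of significant results would come from trials whose estimated school variance is zero or negative, and the report must explain this.

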9.2. General Considerations

9.2.1. Definition of Analysis Populations

All participants who receive the study product will be considered evaluable for the safety population.

All participants in the safety population with any post-treatment assessment will be included in Intent-to-treat (ITT) population. ITT population will be the primary population for efficacy analysis.

Per protocol (PP) population will consist of participants who have all post-treatment assessments and do not have any protocol violations that would affect efficacy assessments. PP analyses will be performed only if there is more than 5% difference between number of study participants in ITT and PP population. A final decision on whether a PP analysis will be performed will be made prior to study un-blinding.

9.2.2. Exclusion of Data from Analysis

Prior to database lock and breaking of the study blind, review listings will be defined and reviewed by the Biostatistician and Medical Director (or designee) to identify protocol violations and to determine their level of impact on efficacy analyses. Further details of these review listings will be provided in the statistical analysis plan (SAP) and review listing specification document. The review listings may include, but will not be necessarily limited to, the following:

- Violation of inclusion or exclusion criteria that are deemed to affect efficacy.
- Use of prohibited treatment (e.g. usage of immunosuppressive therapy *e.g.*, oral corticosteroids or chemotherapy during the course of study) or medication before or during the study, which is felt to affect the assessment of efficacy.

 GlaxoSmithKline	Document Name	Clinical Study Protocol 204477		
	Type	Version	Document Identifier	Effective Date
	eldo_clinical_doc	5.0; Most-Recent; Effective; CURRENT	090032d580daa95e	10-Oct-2017 06:16:49
	Reason For Issue	Auto Issue		

- Non-compliance with product administration.
- Comments.

9.2.3. Criteria for Assessing Efficacy

The study will be deemed to be successful if a statistically significant decrease is demonstrated in number of ill days during nine (9) months of intervention in the test product group compared to the control product of the study.

9.2.4. Criteria for Assessing Tolerability

Safety will be assessed by reporting adverse events (AEs) by all participants taking the test product vs. control product of the study.

9.2.5. Handling of Dropouts and Missing Data

No data will be imputed in case of dropouts or missing data.

9.2.6. Other Issues

There will be no interim analysis.

9.3. Statistical Methods and Analytical Plan

Additional details of the proposed statistical analysis will be documented in the statistical analysis plan (SAP), which will be written following finalisation of the protocol and prior to **STUDY ANALYSIS** ~~study start (first subject first visit (FSFV))~~.

9.3.1. Demographic and Baseline Characteristics

Participant demographics information will include age, gender, and race.

Baseline characteristics will include height, weight, and HAZ.

Categorical measures (gender, race, and HAZ (for ranges: -3 to -2 and -2 to -1)) will be summarised by number and percent of participants in each category.

Descriptive statistics for continuous measures (age, height, weight, BMI and HAZ) will include the number of participants (N), mean, median, standard deviation (SD), minimum, and maximum.

 GlaxoSmithKline	Document Name	Clinical Study Protocol 204477		
	Type	Version	Document Identifier	Effective Date
	eldo_clinical_doc	5.0; Most-Recent; Effective; CURRENT	090032d580daa95e	10-Oct-2017 06:16:49
	Reason For Issue	Auto Issue		

9.3.2. Primary Analyses

The primary efficacy variable of the study is the number of ill days. The number of ill days is defined as number of days a subject is ill because of GI and/or respiratory illnesses as diagnosed by study physician, as per the criteria defined in Section 6.11.1 and 6.11.2, over the intervention period.

For this variable, primary analysis will be performed on participants in ITT population who have completed the entire study for 9 months.

The null hypothesis of interest is:

H₀: There is no difference in the number of ill days.

The alternative hypothesis of interest is:

H₁: There is a difference in the number of ill days.

The number of ill days will be summarised in terms of number (N), mean, standard deviation, minimum, and maximum for both the treatment groups.

The number of ill days will be analysed using the analysis of variance (ANOVA). The ANOVA will have treatment, cluster (school), and gender as fixed effects.

Adjusted means, 95% confidence intervals, within treatment p-values for each treatment group, treatment group difference, 95% confidence interval of the difference and the between-treatment p-values based on the statistical model described above will also be presented.

All statistical tests of hypotheses will be two-sided and will employ a level of significance of $\alpha = 0.05$.

The simulated data used for the sample size calculations were based upon the assumption of a Poisson distribution per study treatment. However, on observation of these simulated data, it was considered that these Poisson distributions were not heavily skewed and, as a result, normal distributions may be assumed. Consequently, a normality assumption has been adopted for both the generation of sample size and the intended approach to the statistical analysis. However, the assumptions of normality and homogeneity of variance will be investigated and violation of these assumptions may be overcome using suitable transformation (for example, log or square root). If transformed data is also non-normal, then alternative analyses relevant to Poisson distributed data will be investigated (further details will be

 GlaxoSmithKline	Document Name	Clinical Study Protocol 204477		
	Type	Version	Document Identifier	Effective Date
	eldo_clinical_doc	5.0; Most-Recent; Effective; CURRENT	090032d580daa95e	10-Oct-2017 06:16:49
	Reason For Issue	Auto Issue		

provided in the SAP). If none of these options are considered appropriate for the data, then appropriate non-parametric tests will be performed.

